VEAP ID NO: 9069

PASS INFORMATION

Title	Non-interventional post-marketing safety study (PMSS) to collect information on hepatic function disorders among Japanese patients with radically unresectable or metastatic renal cell carcinoma treated with pembrolizumab in combination with axitinib.	
Protocol Version identifier	3475-A97/000	
Date of last version of protocol	23-MAR-2020	
EU PAS Register No:	Study has not yet been registered.	
Active substance	L01XC18, monoclonal antibody, pembrolizumab L01XE17, Protein-kinase inhibitors, axitinib	
Medicinal product(s):	Keytruda®, pembrolizumab Inlyta®, axitinib	
Product reference:	EU marketing authorisation number: EU/1/15/1024/001 EU/1/15/1024/002	
Procedure number:	EMA procedure number: EMEA/H/C/003820/II/0069	
Marketing authorisation holder(s) (MAH)	MSD K.K.	
Joint PASS	No	
Research question and objectives	The specific aim of this research study is to collect information on hepatic disorders, including clinical events and/or laboratory elevations with or without hepatic dysfunction among Japanese patients with radically unresectable or metastatic renal cell carcinoma who receive treatment with pembrolizumab in combination with axitinib and to describe treatment and resolution of these adverse events in real-world clinical practice.	
Country(-ies) of study	Japan	

VEAP ID NO: 9069

Author	PPD
	Drug Safety Operations
	PPD
	Drug Safety Operations
	MSD K.K.
	[name]
Merck Final Repository (RCAM) Date	23-MAR-2020
Date of Health Authority Approval of Protocol	The drug-use results survey (DURS) protocol will be reviewed and approved by the Japan Pharmaceuticals and Medical Devices Agency (PMDA) prior to study enrollment.

Protocol/Amendment No.: 3475-A97/000

VEAP ID NO: 9069

TABLE OF CONTENTS

		ORMATION	
		F CONTENTS	
		TABLES	
		FIGURES	
L		ABBREVIATIONS	
1		PONSIBLE PARTIES	
2		FRACT	
3		NDMENTS AND UPDATES	
4		ESTONES	
5		IONALE AND BACKGROUND	
6		EACH QUESTION AND OBJECTIVES	
	6.1	Primary Objectives	
7	6.2	Secondary Objectives	
/	7.1	EARCH METHODSStudy Design	
	7.1 7.2	Setting	
	7.3	Variables	
	7.3		
	7.3	•	
	7.3		
	7.4	Data Sources	
	7.4		
	7.5	Study Size	
	7.6	Data Management	
	7.7	Data Analysis	
	7.8	Quality Control	
	7.9	Limitations of the Research Methods	
8	PRO	FECTION OF HUMAN SUBJECTS	
	8.1	Informed Consent	23
9	MAN	AGEMENT AND REPORTING OF ADVERSE EVENTS/ADVERSE	
	REA	CTIONS	23
	9.1	Adverse Event Reporting	23
	9.1	.1 INVESTIGATOR RESPOSIBILITY	24

1 RESPONSIBLE PARTIES

Contact details for the responsible parties at Merck Sharp & Dohme (MSD) KK and designees (such as contract research organization [CRO]) are available upon request.

2 ABSTRACT

Title	Non-interventional post-marketing safety study (PMSS) to collect information on hepatic function disorders among Japanese patients with radically unresectable or metastatic renal cell carcinoma treated with pembrolizumab in combination with axitinib.	
Protocol Number / Version	3475-A97/000	
Date	23-MAR-2020	
Author	Drug Safety Operations	
	Drug Safety Operations	
	Merck Sharp and Dohme (MSD) KK [name]	
Rationale & Background	In KEYNOTE-426 (KN426), a Phase III randomized, open-label study, treatment with pembrolizumab plus axitinib resulted in significantly longer overall survival and progression-free survival, as well as a higher objective response rate, than treatment with sunitinib, among previously untreated advanced renal cell carcinoma (RCC) patients. The observed safety profiles of pembrolizumab plus axitinib and of sunitinib were as expected on the basis of the known profiles of these three drugs, although the incidence of grade 3 or 4 elevations in liver enzyme levels in the pembrolizumab plus axitinib group was higher than expected given the	
	known safety profiles of each drug when used as monotherapy.	

VEAP ID NO: 9069

	As part of the risk management plan (RMP), the Japanese health authority (Pharmaceutical and Medical Devices Agency [PMDA]) is requesting a drug-use results survey (DURS) to collect information on hepatic function disorders in patients with radically unresectable or metastatic renal cell carcinoma treated with pembrolizumab in combination with axitinib, and to describe treatment and resolution of these adverse events. The DURS is a regulated post-marketing surveillance system unique to Japan to collect information on treatment outcomes in routine clinical practice.
Research Question(s) & Objective(s)	The specific aim of this research study is to collect information on hepatic disorders, including clinical events and/or laboratory elevations with or without hepatic dysfunction among Japanese patients with radically unresectable or metastatic renal cell carcinoma who receive treatment with pembrolizumab in combination with axitinib and to describe treatment and resolution of these adverse events in real-world clinical practice.
Study Design	Prospective, open-label, multicentre, observational, Phase 4 study, conducted in Japan.
Population	Patients with radically unresectable or metastatic renal cell carcinoma treated who receive treatment with pembrolizumab in combination with axitinib
Variables	The primary exposure variables include variables related to administration of pembrolizumab and axitinib including date of administration, dose, discontinuation and interruption of treatment. The primary outcome variables include hepatic disorders including adverse events based on clinical events and/or laboratory elevations. Additional covariate data (e.g., baseline demographic and medical history and concomitant therapies) will also be collected.
Data Sources	Healthcare practitioners will be surveyed for information related to treatment with pembrolizumab in combination with axitinib as used in routine clinical practice.

Protocol/Amendment No.: 3475-A97/000

VEAP ID NO: 9069

Study Size	Data on approximately 150 patients will be collected, as agreed with the Japanese health authority during review of the pembrolizumab RCC marketing application. There is no formal hypothesis testing or power calculation.
Data Analysis	Descriptive statistics will be reported, including measures of central tendency (mean, median) and dispersion (standard deviation, range) for continuous variables and frequency and percentages for categorical variables. Comparison of characteristics in subgroups will be performed using Chi-square test, or Fisher's exact test for categorical/binary variables, and Student's t-test for continuous data. Other test statistics may be used, as relevant, depending on data distributions and normality assumptions.
Milestones	
Start of data collection:	1Q 2020
End of data collection:	1Q 2022
Interim report(s) of study results:	Not required.
Study progress report(s):	Progress of the survey and adverse drug reactions will be created according to JPSUR submission schedule regulated in Japan.
Final report of study results:	1Q 2023

3 AMENDMENTS AND UPDATES

None.

4 MILESTONES

Milestone	Planned Date
Start of data collection	1Q 2020
End of data collection	1Q 2022
Study progress reports	Progress of the survey and adverse drug reactions will be created according to JPSUR submission schedule regulated in Japan
Registration in the EU PAS register	Study will be registered within 35 days of PMDA approval of the protocol.
Final report of study results	1Q 2023

VEAP ID NO: 9069

5 RATIONALE AND BACKGROUND

KEYNOTE-426 (KN426) is a Phase III randomized, open-label study to evaluate the efficacy and safety of pembrolizumab in combination with axitinib versus sunitinib monotherapy as a first-line treatment for locally advanced or metastatic renal cell carcinoma (RCC). [Rini, B. I., et al 2019] In the open-label, Phase 3 trial, 861 chemotherapy-naïve patients with previously untreated advanced clear-cell renal-cell carcinoma were randomized in a 1:1 fashion to receive pembrolizumab (200 mg) intravenously once every 3 weeks plus axitinib (5 mg) orally twice daily (432 patients) or sunitinib (50 mg) orally once daily for the first 4 weeks of each 6-week cycle (429 patients). The study was a multinational study with 24%, 24%, and 52% of patients randomized in North America, Western Europe and Rest of World, respectively. The study included a total of 94 Japanese patients.

After a median follow-up of 12.8 months, the estimated percentage of patients who were alive at 12 months was 89.9% in the pembrolizumab plus axitinib group and 78.3% in the sunitinib group (hazard ratio [HR] for death, 0.53; 95% confidence interval [CI], 0.38 to 0.74; P<0.0001). Among patients with previously untreated advanced RCC, treatment with pembrolizumab plus axitinib resulted in significantly longer overall survival and progression-free survival, as well as a higher objective response rate (ORR), than treatment with sunitinib. Median progression-free survival was 15.1 months in the pembrolizumab plus axitinib group and 11.0 months in the sunitinib group (HR for disease progression or death, 0.69; 95% CI, 0.56 to 0.84; P<0.001). The ORR was 59.3% (95% CI, 54.5 to 63.9) in the pembrolizumab plus axitinib group and 35.7% (95% CI, 31.1 to 40.4) in the sunitinib group (P<0.001). The benefit of pembrolizumab plus axitinib was observed across the International Metastatic RCC Database Consortium (IMDC) risk groups (i.e., favorable, intermediate, and poor risk) and regardless of programmed death ligand 1 expression.

Grade 3 or higher adverse events (AEs) of any cause occurred in 75.8% of patients in the pembrolizumab plus axitinib group and in 70.6% in the sunitinib group. The observed safety profiles of pembrolizumab plus axitinib and of sunitinib were as expected on the basis of the known profiles of these three drugs, although higher than expected given the known safety profile of each drug when used as monotherapy. Approximately 20% (91/429) of patients treated with pembrolizumab plus axitinib experienced grade 3 or 4 hepatic AEs. In KN426, the majority (79.2%, 168/212 patients) of hepatic events (including grade 3 or 4 events) occurred within 6 months of treatment, and majority (68.6%, 24/35 patients) of serious hepatic adverse events resolved within 3 months of occurrence. Within a 9-month period, the majority of hepatic events were observed and resolved during that timeframe. There were no deaths related to hepatic adverse events in the pembrolizumab plus axitinib group.

The use of pembrolizumab in combination with axitinib has been approved in the US, EU and other countries around the world for 1L treatment of RCC, with a recent approval in December 2019 in Japan by the Pharmaceuticals and Medical Devices Agency (PMDA). As condition of approval, the PMDA is requesting a drug-use results survey (DURS), or more specifically a specific use results survey, to collect information on hepatic disorders in Japanese patients who receive the product in real-world clinical practice. The DURS is a regulated post-marketing surveillance system unique to Japan to collect information on treatment outcomes

Protocol/Amendment No.: 3475-A97/000

VEAP ID NO: 9069

in routine clinical practice. This study is not required by the European Medicine's Agency (EMA) but, given the objective to quantify and characterize a specific identified risk as a condition of approval, the MAH considers this a voluntary post-authorization safety study (PASS).

It is important to recognize that different regions and countries have specific requirements and guidance for post-marketing commitment and may name them differently (e.g. post-market surveillance [PMS] studies in Japan and PASS in Europe. [Haque, A., et al 2017] While the overall intent of these studies may be similar, the approach to study design and execution can vary considerably, as a result of different governing regulatory frameworks. In Europe, the development of PASS protocols are guided by the EMA's Guideline on Good Pharmacovigilance Practices, Module VIII; post-market studies. In Japan, however, PMS studies must be conducted in accordance with ministerial ordinance Good Post-market Study Practice (GPSP), which generally allows for five potential designs: 1) general drug-use results survey of all AEs or specific AEs (such as hepatotoxicity), 2) special survey for specific population (such as children), 3) drug use results comparative survey, 4) post-marketing database survey, and 5) post-marketing clinical trials. The GPSP also does not recognize the need to collect data on a comparator drug and does not allow for source data verification (SDV) at participating clinical sites. These and other limitations of Good Pharmacoepidemiology Practice (GPP) does not allow for an unbiased assessment of treatment causality.

Although sufficient rigor will be applied to design and execution of the study described herein, the results of this exploratory analysis should be cautiously interpreted given the noted limitations imposed by the governing local regulatory framework within which this study is to be conducted.

6 RESEACH QUESTION AND OBJECTIVES

The study is exploratory and descriptive in nature. The specific aim of this research study is to collect information on hepatic disorders including clinical events and/or laboratory elevations with or without hepatic dysfunction among Japanese patients with radically unresectable or metastatic renal cell carcinoma who receive treatment with pembrolizumab in combination with axitinib, and to describe treatment and resolution of these adverse events in real-world clinical practice. There is no formal hypothesis testing. These research aims will be addressed with the following specific study objectives.

6.1 Primary Objectives

Among Japanese patients with radically unresectable or metastatic RCC who receive treatment with pembrolizumab in combination with axitinib, to describe the proportion of patients with hepatic disorders, including clinical events and/or laboratory elevations with or without hepatic dysfunction.

Protocol/Amendment No.: 3475-A97/000

VEAP ID NO: 9069

6.2 Secondary Objectives

Among the overall population:

1. To describe the demographic and baseline medical history;

- 2. To describe baseline medication use;
- 3. To describe the proportion of patients who discontinue one or both drugs due to hepatotoxicity (overall, serious and grade 3 or higher), including clinical events and/or laboratory elevations, and time to discontinuation;
- 4. To describe the proportion of patients with one or both drugs interrupted due to hepatotoxicity (overall, serious and grade 3 or higher), including clinical events and/or laboratory elevations, time to interruption, and time to resumption of the index drug (s);
- 5. To describe the proportion of patients with a dose reduction for one or both drugs due to hepatotoxicity (overall, serious and grade 3 or higher), including clinical events and/or laboratory elevations, and time to dose reduction;

Among patients with hepatic disorders (overall, serious and grade 3 or higher), including clinical events and/or laboratory elevations:

- 6. To describe the demographic and baseline medical history;
- 7. To describe baseline and concomitant medication use;
- 8. To describe the proportion of patients with hepatic AEs that resolve;
- 9. To describe the proportion of patients using systemic corticoid steroids and other treatments;
- 10. To describe the time from initiation of pembrolizumab in combination with axitinib to onset of hepatic AEs;
- 11. To summarize the type of hepatic disorders.

Subgroup analyses will be conducted for drug-related adverse events, based on investigator assessed causality.

7 RESEARCH METHODS

7.1 Study Design

The study design is a non-interventional cohort study of Japanese patients with radically unresectable or metastatic RCC treated with pembrolizumab in combination with axitinib. There will be no systematic sampling of patients at each site, and patients approached regarding the study will be at the investigator's discretion. Patients participating in the study will be

Protocol/Amendment No.: 3475-A97/000

VEAP ID NO: 9069

treated according to normal clinical practice and no intervention will be assigned in accordance with the study protocol. In all cases, the decision to treat the patients with pembrolizumab in combination with axitinib will be made by the patient's healthcare practitioner (HCP) prior to the decision to enroll the patient into the study. Given the observational nature of the study, all safety assessments will be performed according to standard clinical practice of each clinical site, and are not mandated by the study design nor protocol.

The index date will be the date of the first prescription or dispensing record for the index drugs including pembrolizumab plus axitinib (Figure 1, below) As a general rule, patients should be registered within 14 days from the starting date of index drug administration (index date, day 0). Healthcare practitioners will be surveyed to collect information on the risk of hepatic events and treatment of those events occurring within 9-months of treatment. Follow-up will continue until the end of the observation period or early termination due to withdrawal of consent, loss to follow-up, death.

The study design includes a 9-month period of observation given that hepatic dysfunction disorders in KN-426 plateaued after approximately 6-months of therapy, and a majority of patients with serious liver-related adverse events recovered within 3-months of follow-up:

[figure not shown]
- In KN426, the incidence rate of hepatic dysfunction was 111 (25.9%) patients within 3 months, 57 (13.3%) patients within 3-6 months, 21 (5.5%) patients within 6-9 months, 15 (4.5%) patients within 9-12 months, and 8 (3.1%) patients after 12 months. 79.2% (168/212) of the patients had hepatic AEs which occurred within 6 months and the incidence did not tend to increase thereafter.
- For Grade 3 or higher hepatic AEs, there were 60 patients (14.0%) patients within 3 months, 20 patients (4.7%) within 3-6 months, 7 patients (1.8%) within 6-9 months, 2 patients (0.6%) within 9-12 months, and 2 patients (0.8%) after 12 months. 87.9% (80 of 91) had hepatic Grade 3 or higher hepatic AEs which occurred within 6 months and the incidence did not tend to increase thereafter.
- In addition, 68.6% (24 of 35) of patients with serious liver-related adverse events recovered within 3 months.
- The resolution of liver-related adverse events could be ascertained by observing the patients for 3 months after onset.

Based on the above, considering the 6 months before onset and the 3 months before resolution, the observation period for this study was set at 9 months. Based on the incidence of hepatic AEs, we anticipate collecting information on approximately 30 patients with Grade 3 or higher events in this survey (see Section 7.5). The Japanese regulatory authority agreed that a 9-month period of observation would be sufficient.

VEAP ID NO: 9069

Figure 1 Study Diagram

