7.4.1 Study Procedures

Patients will be observed from initiation of pembrolizumab plus axitinib until the end of observation due to withdrawal of consent, loss to follow-up, death, or until end of the study period. The study period is intended to extend for up to 9 months after initiation of therapy. Visits will not occur according to a set schedule, and will be driven by clinical management of patients at each site. However, it is expected that site visits will occur approximately every 3 weeks, based on the dosing recommendations for pembrolizumab in the product label.

After the decision by HCP to treat the patients with pembrolizumab in combination with axitinib, patients recruited for the study will consent to study participation, in accordance with local ethics committee requirements. As a general rule, patients should be registered within 14 days from the starting day of the index drugs. Sites will complete and submit a patient

VEAP ID NO: 9069

registration CRF using an electronic data capture (EDC) system, and the CRF will include some baseline information include patient identifier number, gender, year and month of birth or age at the start of treatment, treatment at an inpatient or outpatient facility, starting date of drug administration, and reason for drug use (see Table 1, below). The additional CRFs will be collected and submitted at the end of the 9-month observational period for each patient. Site guidance will be to complete and submit the CRFs within 1 month after the 9-month period of observation, and it is anticipated that an additional 1-2 months will be needed for MAH to query and correct/update entries, as needed (see Figure 1). Training on the EDC data capture system will be performed by the MAH designee (CRO).

After the 9-month period of observation, the CRO will send an email request to the HCP asking him or her to submit the complete CRFs via the EDC system. An email reminder is sent to the site at least once a month until the CRFs are completed and submitted using the EDC system.

Table 1 Schedule for Completion/Submission of Case Report Forms

	Completion and Submission of Registration Forms (guidance is to register	Completion and Submission of Additional Case Report Forms (guidance is to
	patients within 14 days of index date ¹)	complete/submit within one month after the 9-month period of observation)
Name of facility		
Name of department	$\sqrt{}$	
Date of form completion	$\sqrt{}$	

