7.9 Limitations of the Research Methods

Given its observational nature, the study is prone to potential forms of bias including, for example selection bias, surveillance bias and information bias. Also, the results may not be generalizable to patients treated within other countries and healthcare systems.

A potential form of bias for this study is selection bias, which occurs when patients in the study differ systematically from the population of interest (patients with radically unresectable or metastatic RCC), limiting the generalizability of results to the broader patient population. For this study, there will likely be some degree of selection bias given the index drugs are commercially available and patient consent to study participation will be necessary. The descriptive baseline demographic and medical history for patients included in this study can be qualitatively compared with other trial and realworld evidence studies of patients with advanced RCC to help put these results into context.

With the introduction of new drugs for a given indication, there is also the potential for another form of selection or allocation bias due to the channeling of newly marketed drugs to more severe cases. This may result in channeling bias with a higher risk of adverse events being reported than would be expected for the general population of patients receiving drug. Comparison of baseline characteristics with other general RCC study populations may also help in identifying the potential degree of channeling bias.

The study may also suffer from bias due to increased surveillance, screening or testing of the outcome or associated symptoms given the noted primary objective of the study. One way to help with interpretation of results in this instance would be to include a comparator drug to allow for the assessment of relative risk. However, inclusion of a comparator group is not possible in this study given the DURS design and limitations imposed by governing ordinances (GPSP) for these surveillance studies. It is also likely that the outcomes reported for the study

Product: MK-3475 23

Protocol/Amendment No.: 3475-A97/000

VEAP ID NO: 9069

are generally more severe in nature, than otherwise would be observed and potentially attributable to treatment. This bias is hard to address given the observational study design, and is a notable limitation of this study.

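### Registration at the investigator's choice, after the first dose and with no firm limit, can depend on an early hepatic event; separately, the index date has two definitions

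*Protocol*

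**What the plan says.** On who enters, Section 7.1 states: "There will be no systematic sampling of patients at each site, and patients approached regarding the study will be at the investigator's discretion". The decision to treat comes before the decision to enrol. Section 7.2.1 enrols patients who have already had at least one dose and sets no exclusion criteria.

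On when they enter, Section 7.1 gives the soft 14-day rule: "As a general rule, patients should be registered within 14 days from the starting date of index drug administration (index date, day 0"). Section 7.4.1 repeats it ("As a general rule, patients should be registered within 14 days from the starting day of the index drugs"), and Table 1 labels it guidance. No latest registration date is stated, nor what happens to a patient registered after it.

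On what is counted, Section 7.4.1 observes patients from treatment initiation. The primary objective (Section 6.1) is the proportion with hepatic disorders.

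On bias, Section 7.9 says that "there will likely be some degree of selection bias given the index drugs are commercially available and patient consent to study participation will be necessary". It adds channelling and increased surveillance, and proposes comparing baseline characteristics with other RCC studies.

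On day 0, Section 7.1 first says "The index date will be the date of the first prescription or dispensing record for the index drugs including pembrolizumab plus axitinib". The next sentence ties the same label to the "starting date of index drug administration (index date, day 0"). The footnote to Table 1 does not say whether prescription, dispensing or administration is meant.

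**The concern.** The primary result is an absolute risk in a single cohort, so it depends directly on who is in the denominator. The investigator chooses whom to register, knows that the study is about liver events, and may choose after treatment has begun. A patient may then be registered because a hepatic event has already appeared, or left out because the early course made consent or follow-up difficult. The first raises the proportion and the second lowers it. The confidence interval reflects neither, and a larger sample removes neither.

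The index date is a separate matter. The 14-day rule, the 9-month window, the baseline period (Section 7.3.3) and time to onset (Section 6.2, objective 10) all need one origin. An infusion and an oral drug need not start on the same day.

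**Working it through.** **Inputs from the protocol.** KN426 patients with hepatic events, by time of onset (Section 7.1): 111 within 3 months, 57 at 3–6 months, 21 at 6–9, 15 at 9–12 and 8 later. These sum to 212, and 212/429 = 49.4%, as Section 7.5 states. Also 111/429 = 25.9%, as stated. The crude 9-month share is (111 + 57 + 21)/429 = 189/429 = 44.1%.

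**Inputs that must be assumed.** The protocol gives neither the share of onsets before registration nor how an early event changes the chance of registration. I take 3 months as 91 days with onsets spread evenly, and a relative chance of registration r of 0.5 to 2 for patients whose onset precedes registration.

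**Formula.** With P the true proportion, e the share of patients with onset before registration, and r as above, the observed proportion is

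P′ = (P − e + r·e) / (1 − e + r·e).

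If r = 1, then P′ = P.

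**14 days kept.** Early cases: 111 × 14/91 = 17.1 of 429, so e = 4.0%.
- r = 0.5: (189 − 8.5)/(429 − 8.5) = 42.9%
- r = 2: (189 + 17.1)/(429 + 17.1) = 46.2%

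The shift is about −1 to +2 points.

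**Other shares of the 3-month onsets falling in the first 14 days (assumed), same r:**

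| Share in first 14 days | e | r = 0.5 | r = 2 |
|---|---|---|---|
| 5% | 1.3% | 43.7% | 44.8% |
| 15% (even spread) | 4.0% | 42.9% | 46.2% |
| 30% | 7.8% | 41.8% | 48.1% |

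**Scale.** The exact 95% interval for 74/150 (the KN426 overall rate at the planned N) is 41.1% to 57.6%, a half-width of about 8 points.

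**Effect of excluding patients with an event before registration.** Suppose there is no selection at all and everyone is registered on day 14. Dropping patients with an earlier event gives (189 − 17.1)/(429 − 17.1) = 41.7% instead of 44.1%. The exclusion alone lowers the estimate by 2.4 points, as much as the bias it is meant to reveal.

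**Whether the baseline comparison helps.** Baseline covariates are measured before the index date. Two cohorts can match on all of them and still differ in whether registration depended on an event after treatment start.

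**Index date, side by side.** Definition 1 is the first prescription or dispensing record. Definition 2 is the start of administration. The exposure data (Section 7.3.1) include date of first dose, and the registration form (Table 1) includes starting date of administration. No prescription or dispensing date is listed. Definition 2 is therefore the one the planned data support. Neither definition says which date applies if the two drugs start on different days.

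**The case against.** The strongest reply is that the effect is small and largely disclosed. The 14-day period appears three times, and nothing in the protocol suggests long delays. Under even spread only 17.1 of the 212 KN426 patients with hepatic events (8%) have onset by day 14. Stopping early does not bar registration, and KN426 had no deaths related to hepatic events in this arm. The study is descriptive, Section 7.9 concedes selection bias and asks for very cautious interpretation, and Section 7.7 leaves sensitivity analyses to the SAP. All of this limits the size. It does not remove the mechanism: who may be registered, and until when, are conduct rules that an analysis plan cannot repair afterwards. A firm 14 days would also usually fall before the first follow-up visit, expected at about 3 weeks; a general rule lets registration slip past it.

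Four stronger readings are tempting and not supported:
- **A large bias.** If registration slipped to 6 weeks for everyone, then e = 111 × (42/91)/429 = 11.9% and the same r would give 40.5% to 50.0%. That delay is hypothetical; the protocol neither plans nor predicts it.
- **That hepatic events concentrate before registration.** The 8% above says otherwise if 14 days is kept.
- **That the two index dates cause the selection.** They do not. They blur the time origin, and most of the text already points to administration or initiation. One sentence is out of line, and the figure it refers to is not available here.
- **That Section 7.9 is silent on selection.** It is not; it omits this one mechanism.

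**Conclusion.** The point holds in limited form. Discretionary approach, registration after the first dose and a 14-day rule without a firm limit allow entry to depend on a hepatic event that then counts toward the primary proportion. The direction is unknown. Any figure for the size rests on the assumptions above: about 43% to 46% around a true 44.1% if 14 days is kept, small beside a half-width of about 8 points, and larger if registration runs later. The conflicting index-date definitions are a separate wording defect that needs reconciling. Both are worth correcting because correction is cheap and the bias cannot be removed once the data are in.

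**What to change.** 1. In Sections 7.1 and 7.4.1, have each site register consecutive eligible patients from the start of its contract.
2. Make 14 days a firm limit for the primary analysis set. Report later registrations separately, and show the primary proportion with and without them.
3. Record whether a hepatic AE preceded registration and report the number. The event date (Section 7.3.2) and the completion date of the registration form (Table 1) are already planned items. Do not exclude patients because of such an event, since that lowers the proportion even without selection.
4. Name this mechanism in Section 7.9.
5. Use one index-date definition in Section 7.1, Section 7.4.1 and Table 1, based on the administration date the CRF already collects, and state which date applies when the two drugs start on different days.

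The cost is protocol and site-instruction wording and one additional table. The downside is less flexibility for sites and possibly somewhat slower accrual. The planned 150 analysed and 200 enrolled need not change.
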